2.0 CLINICAL TRIAL OBJECTIVES

We will test, for the first time, the overall feasibility of bilateral accelerated deep transcranial magnetic stimulation (deep aTMS) for smoking abstinence, including measures of tolerability, acceptability, retention, and adherence. Our secondary objectives are to assess the effects of deep aTMS on short-term point prevalence abstinence—measured by self-reported abstinence over the past 7 days and confirmed with urine cotinine—at the end of treatment (Week 1), and at Weeks 3, 5, 9, 13, and 26, as well as prolonged and continuous abstinence rates at Weeks 13 and 26. We also aim to explore the potential for rapid onset of effect, along with its impact on attenuating craving, reducing cigarette consumption, and decreasing dependence severity throughout the study.

2.1 Primary Objectives

To assess the overall feasibility of bilateral accelerated deep TMS (aTMS) for smoking abstinence, including measures of tolerability, acceptability, retention, and adherence.

2.2 Secondary Objectives

Secondary Aim 1: To examine the effect of bilateral deep aTMS on short-term abstinence at the end of TMS treatment, at post-treatment follow-ups (point prevalence abstinence at Week 3, Week 5, Week 9, Week 13, Week 26),

Secondary Aim 2: To examine the effect of bilateral deep aTMS on prolonged and continuous abstinence at 3-month and 6-month follow-up (Week 13 and Week 26).

Secondary Aim 3: To examine the effect of bilateral deep aTMS on other smoking outcomes throughout study duration including self-reported craving, cigarette smoking and dependence severity.

3.0 CLINICAL TRIAL DESIGN

3.1 Overall Design

This clinical trial is designed as a one-arm, open-label study to evaluate the efficacy and feasibility of the H4 deep accelerated transcranial magnetic stimulation (aTMS) protocol for smoking cessation. The absence of a control group is intentional, as this pilot study focuses on assessing the intervention's preliminary efficacy in a single arm of 40 participants with tobacco use disorder who are motivated to quit, aiming for 30 completers to guide a future controlled trial. Each participant's involvement will last 26 weeks, starting with a screening phase at Week 0, followed by a one-week treatment period in Week 1, and concluding with follow-up visits at Weeks 3, 5, 9, 13, and 26. The entire trial is expected to span approximately 2 years, covering recruitment, treatment, and follow-up for all participants.

During Week 1, participants will receive 20 rTMS sessions using the Health Canada-approved H4 deep TMS coil, administered at four sessions per day over five consecutive days, targeting the insular cortex, alongside brief counseling adapted from the Mayo Clinic's 'Smoke Free and Living It' manual. Daily assessments will monitor safety, Timeline Followback (TLFB), and nicotine craving and withdrawal symptoms. The primary outcome is overall feasibility, including measures of tolerability, acceptability, retention, and adherence. Secondary outcomes include 7-day point prevalence abstinence—verified by self-report and urine cotinine levels (<200 ng/mL)—at the end of treatment and at Weeks 3, 5, 9, 13, and 26. We will also assess 3-month abstinence at Week 13 and 6-month abstinence at Week 26, both verified by continuous self-reported abstinence during

the respective periods and corresponding urine cotinine levels. Factors such as comorbidities, pre-existing tobacco use disorder severity, or motivation level for abstinence may influence results; these are addressed through eligibility criteria and statistical adjustments.

It is anticipated that a proportion of enrolled participants may not proceed to the treatment phase (Week 1) due to scheduling, logistical, or personal factors. These individuals will be classified as early dropouts and excluded from the intent-to-treat analysis, which will include only participants who initiate at least one TMS session.

3.2 Primary Endpoints

The overall feasibility of accelerated deep TMS (aTMS) for smoking abstinence: assessed through tolerability (frequency of side effects reported at each visit during Week 1), acceptability (self-reported ratings collected at the end of treatment), retention rate (the proportion of participants who completed the full study), and adherence rate (the proportion of completed sessions among participants who initiated treatment).

3.3 Secondary Endpoints

1. Proportion of participants achieving 7-day point prevalence abstinence at end of treatment, Week 3, Week 5, Week 9, Week 13, and Week 26.
2. Proportion of participants achieving prolonged and continuous abstinence at Week 13 and Week 26.
3. Change in self-reported craving, average cigarettes smoked per day, and dependence severity (e.g., using standardized questionnaires) from baseline through study completion.

4.0 PARTICIPANT SELECTION, RECRUITMENT AND WITHDRAWAL

4.1 Target Population

This trial targets 40 adults (aged 18-65) with tobacco use disorder who smoke ≥ 10 cigarettes daily, have an FTND score ≥ 4 , and a Contemplation Ladder score ≥ 7 , aiming for 30 completers. Pregnant people, children, cognitively impaired individuals (MMSE < 24), and those with rTMS safety concerns, such as underlying neurological diseases or a history of seizures or suicidal behavior, are excluded.

4.2 Participant Recruitment and Screening

Recruitment: Participants in the proposed study will be individuals with tobacco use disorder (n=40). The anticipated accrual rate is approximately 20 participants per year. With a target sample size of 40, we expect to complete enrollment over a period of 2 years. We will recruit through various sources: local newspaper ads, the community, Waypoint Centre for Mental Health Care, and Sunnybrook Health Sciences Centre clinics, word of mouth, and/or through posters/flyers distributed in and around the research sites. Approved study recruitment ads will be placed primarily around, but not limited to, the Midland-Penetanguishene and downtown Toronto areas to target participants who can feasibly travel to either study site. In Toronto, ads may also be placed in TTC streetcars, buses and subways. Ads and flyers will be approved by the REB. Participants may also be recruited from similar protocols approved at each research center provided they have agreed to being contacted about future studies.

Eligibility Screening: Potential participants will undergo Waypoint or Sunnybrook REDCap pre-screening to determine initial eligibility. They will subsequently be invited to an in-person or remote Screening Assessment to confirm final eligibility to participate. Following the review and signing of the Informed Consent Form, the following measures and assessments will be administered at the screening visit:

- 1) Fagerstrom Test of Nicotine Dependence (FTND). The FTND is a measure of physical dependence severity.
- 2) Mini International Neuropsychiatric Interview (MINI). MINI will be used to diagnose tobacco use disorder in participants and/or any other psychiatric issues.
- 3) Smoking Contemplation Ladder. This questionnaire allows for the measure of readiness to quit smoking in individuals. A cutoff score of 7 is commonly used to determine individuals who are motivated to quit.
- 4) Medical and/or psychiatric assessment by study physician (or delegate).
- 5) Demographic and contact forms.
- 6) TASS form (TMS Adult Safety Screening Questionnaire).
- 7) Concomitant medication log.

Compensation: Participants who complete the full study will receive a total compensation of \$550, provided either in cash (in CAD) or as an electronic gift card (e.g., EverythingCard). This amount comprises \$25 for the screening and baseline visit each, \$250 for the series of accelerated rTMS visits (\$50 per visit for five visits), and \$50 for each of the five follow-up visits.

4.3 Equity, Diversity and Inclusion Considerations

This study aims to recruit a diverse sample that reflects Ontario's population, ensuring the inclusion of historically underserved groups from various socioeconomic backgrounds. Given that we will also be recruiting participants at Sunnybrook Health Sciences Centre in Toronto, the most multicultural city in Canada, we anticipate strong minority group inclusion and will implement recruitment strategies that promote participation without restrictions based on race or ethnicity. Additionally, in alignment with Waypoint Centre for Mental Health Care's Equity, Diversity, and Inclusion strategy, we will integrate training on Indigenous Cultural Safety, Anti-Black Racism, and EDI principles to foster an inclusive research environment. Recruitment and retention strategies will also be designed to ensure that our research team and staffing reflect the diverse patient populations we serve.

Recognizing that sex and gender differences influence addiction and treatment outcomes, our study will integrate sex- and gender-based analysis to ensure a comprehensive approach to data interpretation. We will collect and analyze self-reported biological sex and gender identity to assess potential differences in treatment efficacy and interpret findings through a sex- and gender-based lens, ensuring that our recommendations remain relevant across diverse populations. Given established sex-related differences in smoking behaviors and nicotine metabolism, we will make every effort to recruit an equal number of male and female participants for robust sex-based analyses. Additionally, studies have shown that hormonal fluctuations can influence rTMS effects, with women exhibiting greater sensitivity to stimulation during periods of high estrogen. To ensure safety, pregnant or breastfeeding individuals will be excluded, as the safety of deep TMS in these populations has not been established.

4.4 Eligibility Criteria

4.4.1 Inclusion Criteria

The participant must meet all of the inclusion criteria to be eligible for this clinical trial:

1. Aged 18 years or older;
2. Tobacco use disorder as assessed by DSM-5;
3. Fagerstrom Test of Nicotine Dependence (FTND) ≥ 4 ;
4. Reported motivation to quit within 30 days as assessed using the Contemplation Ladder score of ≥ 7 ;
5. Must sign and date the informed consent form;
6. Stated willingness to comply with all study procedures.
7. Able to communicate in English.

4.4.2 Exclusion Criteria

An individual who meets any of the following criteria will be excluded from participation in this clinical trial:

1. Reported smoking abstinence in the 3 months preceding screening visit;
2. Current use of other smoking cessation aids;
3. Contraindication to rTMS;
4. Pregnancy, trying to become pregnant or breastfeeding;
5. Current or recent history of cerebrovascular disease;
6. Unstable major psychiatric disorder(s) (i.e. Axis I Disorders) that would prevent participation in the study at PI (or its delegate) discretion;
7. Serious current or personal history of medical condition/disease (neurological disorders, brain lesions, multiple sclerosis, head trauma, loss of consciousness, hearing loss, etc.) preventing same inclusion as per PI (or its delegate) discretion;
8. Current, personal history or family history of seizures;
9. Concomitant use of medication that lowers seizure threshold, such as clozapine;
10. Concomitant use of more than 2 mg lorazepam (or an equivalent) or any anticonvulsants.

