Follow-up period (Week 13 and 26)

During the Week 13 and 26 visit, a urine cotinine test and TLFB will be administered to determine prolonged abstinence and continuous abstinence. Three-month or six-month prolonged abstinence is defined as abstinence from the end of treatment (W1D5) to the end of follow-up (Week 13 or 26), while three-month or six-month continuous abstinence is defined as abstinence from the target quit day (in Week 1) to the end of follow-up (Week 13 or 26). Assessments for nicotine dependence, withdrawal, craving, and symptoms of depression, anxiety, and mania will also be performed.

- Concomitant medication log, recorded by its generic name, dosage, and dosing frequency
- Timeline Follow-Back (TLFB) – Amount of cigarette used every day since the last follow-up
- Fagerstrom Test of Nicotine Dependence (FTND). The FTND is a measure of physical dependence severity.
- Tobacco Craving Questionnaire-Short-Form (TCQ-SF), to measure smoking craving.
- Minnesota Nicotine Withdrawal Scale (MNWS), to measure the nicotine withdrawal symptoms.
- Patient Health Questionnaire (PHQ-9), to track the possible effects of TMS on depression symptoms.

- General Anxiety Disorder-7 (GAD-7), to track the possible effects of TMS on anxiety symptoms.
- Altman Self-Rating Mania Scale (ASRM), to track the possible effects of TMS on developing manic/hypomanic symptoms
- Adverse event log
- Urine cotinine test (threshold: 200 ng/ml)
- Brief counseling for smoking cessation, adapted from the Mayo Clinic's 'Smoke Free and Living It' manual.

All assessments and surveys during research visits can be completed in one of two ways, based on participant preferences or each site's standard data collection practices:

1. **Paper option:** Assessments and surveys printed from REDCap will be completed by hand. A study delegate will review the paper source for completeness and accuracy and enter the data into REDCap.
2. **Electronic:** A study delegate will log into REDCap and will remain present while the participant enters their responses to assessments on an electronic device (e.g., computer, iPad). The study delegate will review the assessment for completeness before saving and help the participant navigate to the next assessment or survey, as necessary.

Procedures for addressing active suicidal ideation during research visits can be found in [Section 8.5 \(Safety Management Plan\)](#).

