6.2 Schedule of Events

Below is the table outlining the assessments, measures, and treatments done at each visit.

	Screening	Baseline	Treatment					Follow-ups				
Week			W1					W3	W5	W9	W13	W26
Visit Code/Number	SC	BL	W1D 1	W1D 2	W1D 3	W1D 4	W1D 5	W3	W5	W9	W13	W26
Assessments & Measures	In-person visit		X	X	X	X	X	X	X	X	X	X
	ICF	X										
	Contact & Demographic Form	X										
	Medical history	X										
	MINI	X										
	TASS	X										
	Smoking Contemplation Ladder	X										
	Quit day plan	X										
	Concomitant Medication Log	X	X					X	X	X	X	X
	Urine Drug Panel		X	X				X				
	Urine Pregnancy Test (if required)			X	X			X				
	TLFB(Cigarettes)		X	X	X	X	X	X	X	X	X	X
	FTND	X	X					X	X	X	X	X
	TCQ-SF (regular or pre-TMS)		X	X	X	X	X	X	X	X	X	X
	TCQ-SF (post-TMS)			X	X	X	X					
	MNSW		X	X	X	X	X	X	X	X	X	X
	PHQ-9		X					X	X	X	X	X
	GAD-7		X					X	X	X	X	X
	ASRM		X					X	X	X	X	X
	AE Log			X	X	X	X	X	X	X	X	X
	Counseling			X				X	X	X	X	X
	Urine cotinine test		X					X	X	X	X	X
	Confirm eligibility			X								
Treat	TMS Experience Questionnaire							X				
	Point Prevalence Abstinence							X	X	X	X	X
	Prolonged Abstinence										X	X
	Continuous Abstinence										X	X
Treat	RMT for TMS			X								
	TMS			X	X	X	X					

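### Abstinence combines a cigarettes-only self-report with a cotinine test that detects nicotine from any source, and other nicotine use is neither excluded nor recorded, so a positive cotinine in someone reporting no cigarettes cannot be interpreted

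*Protocol*

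**What the plan says.** **Who can enter.** Protocol 4.4.1 asks for "Tobacco use disorder as assessed by DSM-5" together with an FTND threshold and a motivation threshold. Section 4.1 describes people who "smoke ≥ 10 cigarettes daily, have an FTND score ≥ 4". Neither requires that cigarettes be the only product. In 4.4.2 the one exclusion that touches nicotine products is "Current use of other smoking cessation aids". The term is not defined.

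**What counts as success.** Section 2.0 defines point prevalence abstinence as "self-reported abstinence over the past 7 days and confirmed with urine cotinine". Section 3.1 gives the cutoff: "verified by self-report and urine cotinine levels (<200 ng/mL"). For the 3-month and 6-month measures, 3.1 requires uninterrupted self-reported abstinence over "the respective periods and corresponding urine cotinine levels".

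**What is recorded.** At each visit where it is given, 6.1 describes the TLFB as "Amount of cigarette used every day since the last follow-up". The Schedule of Events in 6.2 labels it "TLFB(Cigarettes"). The urine drug panel covers opioids, stimulants and alcohol. Section 5.6 asks participants not to start cessation medication, but only over a 13-week course, whereas cotinine is tested up to Week 26.

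**The concern.** Cotinine is a metabolite of nicotine and does not show which product the nicotine came from. A participant can therefore stop cigarettes completely, report that truthfully on the TLFB, and still fail verification because of another product that the eligibility rules allow and no form asks about.

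Abstinence is a secondary endpoint, and none of the four feasibility measures in 3.2 uses cotinine. Even so, section 7.1 justifies the number of completers by the wish to estimate abstinence rates, and 3.1 says the pilot is to guide a controlled trial. A rate that mixes continued smokers with ex-smokers who use another nicotine product is a weaker basis for that planning. A statistical analysis plan can set rules for analysing discordant results, but it cannot supply product-use data that were never collected.

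**Working it through.** The protocol states no figure on this point, so there is nothing to reproduce. The check applies the written rules to a case and then sizes one such case.

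**Step 1: apply the rules to an eligible dual user who stops cigarettes and keeps the other product.**

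| Step | Rule | Result |
|---|---|---|
| Entry | 4.4.1 and 4.4.2 | Eligible, if the product is not used as a cessation aid |
| Self-report | TLFB, cigarettes (6.1, 6.2) | Zero cigarettes: abstinent |
| Cotinine below 200 ng/mL | 3.1 | Verified: abstinent |
| Cotinine at or above 200 ng/mL | 3.1 | Not verified: non-abstinent |
| Source of the nicotine | No form | Unknown |

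The misscoring depends on the cotinine level. A light user of the other product may fall below the cutoff and be scored abstinent.

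**Step 2: what the collected data can show.** The TLFB and urine cotinine are both taken on the fifth treatment day and at Weeks 3, 5, 9, 13 and 26. A result of zero cigarettes with positive cotinine can therefore be identified and counted as the plan stands. It cannot be divided into false reporting and other nicotine use. The medication log could capture nicotine replacement, but nothing in the protocol has it ask about vaping, pouches or smokeless tobacco. No second marker is planned.

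**Step 3: size of one case.** Sections 3.1 and 7.2 analyse abstinence in everyone who receives at least one TMS session. The plan enrols 40 and aims for 30 completers.

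- If 40 are treated: 1/40 = 2.5 percentage points.
- If 30 are treated: 1/30 = 3.3 percentage points.

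**Step 4: illustration under assumptions.** Let *s* be the share of cigarette quitters whose cotinine stays at or above the cutoff because of another product. Then observed rate = true rate × (1 − *s*). The documents give neither the true rate nor *s*; both are assumed here.

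| Assumed true rate | *s* = 5% | 10% | 20% | 30% |
|---|---|---|---|---|
| 50% | 47.5% | 45% | 40% | 35% |
| 30% | 28.5% | 27% | 24% | 21% |

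For scale, 15 abstinent out of 30 has an exact 95% confidence interval of 31.3% to 68.7%. Except at the high end of *s*, the shift is well inside the sampling uncertainty. Unlike that uncertainty, it would not shrink in a larger trial using the same definition.

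**The case against.** **Abstinence may be meant as freedom from all nicotine.** The disorder treated is tobacco use disorder, and the rationale in 1.3 speaks of reducing nicotine use. A positive cotinine would then be a correct failure. This possibility stands, because the protocol does not say which target it intends. It moves the mismatch without removing it: a cigarettes-only TLFB would then be the wrong self-report, and the prolonged and continuous measures, which rely on self-report between visits, would miss other nicotine use.

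**A site could treat a vape or pouch as a cessation aid and exclude the user.** It could, since participants must be motivated to quit and the site investigators decide final eligibility. With the term undefined and two sites, this is not assured. Section 5.6 refers to medications intended to aid cessation, which leaves other use uncovered.

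**The consequence is limited.** This is correct. Abstinence is secondary, and the pilot has no hypothesis test or success threshold.

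**Stronger readings that the documents do not support.**

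- A reader might infer that every dual user who quits fails at every visit. That holds only where cotinine stays at or above the cutoff. Also, the quit date is normally the first treatment day, so the 7-day window ending on the fifth day reaches back before it. Someone who smoked until the quit date fails that visit with or without another product.
- A reader might infer that the error is undetectable. Discordant cases can be counted, and a rate based on self-report alone can be calculated. Only the cause is lost.
- A reader might multiply an assumed dual-use share of 10% to 30% by an assumed one half who quit cigarettes but keep the other product, and report an understatement of 5 to 15 points. Both shares lie outside the documents, and the sum further assumes that all of these people exceed the cutoff.
- A reader might conclude that dual users must be excluded. Section 4.3 aims for a sample representative of the province, and recording the other product is enough to allow attribution.

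**Conclusion.** The point holds as a mismatch between eligibility, the self-report and the biochemical criterion. Under the written rules, an eligible dual user who has stopped cigarettes is scored non-abstinent at any visit where cotinine remains at or above 200 ng/mL, and the data cannot separate that person from someone misreporting cigarettes. If abstinence means cigarettes, the error lowers the rate by 2.5 points per case with 40 treated, or 3.3 points with 30. The number of cases is unknown from the documents, so no total bias can be stated. The conclusion assumes only that some enrolled participants use another nicotine product and that cotinine does not identify its source. The point deserves correction before enrolment, because the missing information cannot be reliably recovered later. It does not threaten the primary feasibility endpoint.

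**What to change.** 1. At baseline and at every visit where the TLFB is given, extend it from cigarettes to any nicotine or tobacco product. Include nicotine replacement, because the request in 5.6 covers 13 weeks and cotinine is tested to Week 26.
2. State in 3.1 and 3.3 whether abstinence means abstinence from cigarettes or from all nicotine, for the point prevalence, prolonged and continuous measures alike.
3. Keep the cotinine-verified rate, and add a sensitivity rate in which participants with zero cigarettes, positive cotinine and recorded other nicotine use are shown separately from other discordant cases.

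The cost is one added item per visit on an existing form. The sensitivity rate will rest on self-report alone for those participants, so it should accompany the verified rate and not replace it. Excluding regular users of other nicotine products is optional: it would make cotinine easier to interpret, but it narrows recruitment and the range of people the results describe.

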4.5 Lifestyle Considerations

- Refrain from use of unregulated or illicit substance use during the rTMS treatment course. If there is use of any of these substances they will be assessed by a study physician to ensure that they are safe to continue with treatment.
- Refrain from problematic alcohol use that includes frequent and recent binge drinking (5 or more drinks on an occasion for men or 4 or more drinks on an occasion for women), the presence of significant alcohol withdrawal symptoms, unpredictable pattern of use with varying amounts of drinking, and in the high-risk category according to low-risk drinking guidelines. Any of these signs will require assessment by a study physician.
- Cannabis use will be assessed prior to treatment start. In general, they will be advised not to make any abrupt changes to their cannabis use without informing the study team. Those that show up visibly intoxicated or in withdrawal from any substance, including cannabis, will need to be seen by a study physician to ensure safety and whether they are appropriate to continue in the trial. Recreational cannabis use is not prohibited as long as they are not exhibiting signs of problematic cannabis use that would destabilize them medically or psychiatrically.
- If problematic substance use as above should arise during the trial, to notify the principal investigator to manage with any other clinical care providers connected to the participant. Emergency medical services will be accessed as needed. Withdrawal from the trial will be determined based on inclusion/exclusion/withdrawal criteria and safety considerations at the discretion of the PI and study team.
- Cigarette smoking induces the liver enzyme CYP1A2, and thus increases metabolism by certain medications that are metabolized by CYP1A2[59]. Participants that are on

these medications will be reviewed to determine whether dose reductions may be needed if patients reduce their cigarette smoking during the treatment course.

- As well, patients with diabetes will also be instructed to monitor their blood sugars more regularly due to the variable effects of smoking cessation on blood sugar control and insulin sensitivity[60].

